5.4.2. Exposure

No imputation will be done for first dose date. Date of last dose of study drug, if unknown or partially unknown, will be imputed as follows:

If the last date of study drug is completely missing and there is no End of Treatment eCRF page and no

Template No.: NVA_TP_CR694 Revision 4 Reference: SOPCR008, WPCR013 Template Effective Date:15Feb2023 Page 13 of 46

Pfizer Inc. / Protocol: C4971002 (TTI-622-02) IQVIA Biotech (Confidential) Project # ZZA82397

death date, the participant should be considered to be ongoing and use the cut-off date for the analysis as the last dosing date

- If the last date of study drug is completely or partially missing and there is EITHER an End of Treatment eCRF page OR a death date available (within the cut-off date), then imputed last dose date is:
 - = 31DECYYYY, if only Year is available and Year < Year of min (EOT date, death date)
 - = Last day of the month, if both Year and Month are available and Year = Year of min (EOT date, death date) and Month < the month of min (EOT date, death date)
 - = min (EOT date, death date), for all other cases.

5.4.3. Last Known Alive Date

The last known alive date will be derived for participants not known to have died at the time of analysis using the latest complete date among the following:

- All patient assessment dates (blood draws (laboratory, PK), vital signs, performance status, ECG, tumor assessments)
- Start and end dates of anti-cancer therapies administered after study treatment discontinuation
- · AE start and end dates
- · Last date collected on the 'Survival status' eCRF
- Study drug start and end dates
- Withdrawal of consent date
- Date of treatment or study discontinuation (do not use if reason for discontinuation is lost to follow-up).

Only dates associated with actual examinations of the participant will be used in the derivation. Dates associated with a technical operation unrelated to participant status such as the date a blood sample was processed will not be used. Assessment dates after the cut-off date will not be applied to derive the last contact date.

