- k. PF-07901801 is administered intravenously through a free-flowing catheter; the duration of infusion is dependent on dose level: dose levels less than or equal to 33 mg/kg infused over 60 min and doses greater than 33 mg/kg infused over 90 minutes and will have doses equal to or less than 2500 mg in 250 mL and doses 2501 mg or more in 500 mL or neat drug if the drug volume is over 500 mL. Prophylaxis for potential infusion-related reaction in accordance with institutional guidelines is acceptable. If Cycle 1 loading doses are implemented, all dosing and lab schedules for the 48 mg/kg dose will follow the schedules for dose levels 12 mg/kg and 24 mg/kg
- l. Detailed sample collection schedule provided in Table 30
- ll Detailed sample collection schedule provided in Table 29
- m. Detailed sample collection schedule provided in Table 32
- n. Detailed sample collection schedule provided in Table 31
- o. Detailed sample collection schedule provided in Table 32
- p. Assessed every 12 ± 2 weeks; telephone contact is acceptable
- q. Newly-acquired FFPE/NBF tumor tissue (tumor block preferred; if tumor block is not available, unstained slides are acceptable). Tumor tissue to be collected anytime after signing of informed consent and prior to treatment on Cycle 1 Day 1. Archival tissue from most recent biopsy is acceptable if fresh tissue specimen is not available at screening. The baseline tissue chosen should be the most recently collected specimen before the start of the study therapy and after the most recent systemic therapy. Detailed sample collection schedule provided in Table 32
- r. Does not need to be performed if previous assessment was within 72 previous hours
- s. Participants should be observed for one hour after infusion with vital signs assessment in 30-minute intervals for signs of infusion-related reaction in Cycle 1; the observation period may be removed at the investigator's discretion in participants who tolerate the infusion well and do not experience infusion-related reaction during Cycle 1.
- t. Target date for FFPE/NBF tumor tissue collection date is Cycle 2 Day 1 but can be collected anytime within 7 days prior to and up to 14 days after Cycle 2 Day 1 (i.e. Tumor tissue should be collected within a 21-day window); other times may be acceptable after consultation with sponsor; tumor block preferred; if block is not available, unstained slides are acceptable. Detailed sample collection schedule provided in Table 32

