- Vital signs (temperature, blood pressure, pulse rate, and respiratory rate)
- Serum chemistry (unless previous assessment was performed within previous 72 hours)
- Hematology (unless previous assessment was performed within previous 72 hours)
- Administer PF-07901801 (12 mg/kg, 24 mg/kg, 48 mg/kg)
- Adverse events
- Concomitant medications and procedures

End-of-Treatment Visit (7 \pm 3 days after last administration of study treatment)

- Complete physical examination
- Vital signs (temperature, blood pressure, pulse rate, respiratory rate, weight)
- Adverse events

- Concomitant medications and procedures
- Blood collection for PF-07901801 concentration
- Blood collection for PF-07901801 anti-drug antibodies

Safety Follow-Up Visit (30 + 5 days after last administration of study treatment or before initiation of subsequent anti-cancer therapy, whichever occurs soonest)

- Complete physical examination
- Vital signs (temperature, blood pressure, pulse rate, respiratory rate, weight)
- ECOG PS
- Serum chemistry (unless performed within previous 72 hours)
- Hematology (unless performed within previous 72 hours)
- 12-lead ECG
- Urine or serum pregnancy test (female participants of childbearing potential only) and counseled on appropriate contraception
- Radiologic assessment of disease status (unless performed within previous 7 days)
- Adverse events
- Concomitant medications and procedures
- Blood collection for CA-125
- Blood collection for PF-07901801 concentration
- Blood collection for PF-07901801 anti-drug antibodies

Long-Term Follow-Up Period

- Radiologic assessment of disease status (participants who have not experienced disease progression)
- Participants with an unresolved AE at the Safety Follow-Up visit considered possibly related to ADA formation may be asked to return to the clinic for ADA blood sampling at approximately 3-month intervals (if feasible given the underlying disease) until the AE or its sequelae resolve or stabilize at a level acceptable to the investigator and sponsor up to a maximum of 12 months.
- Survival and initiation of new anti-cancer therapies (assessed every 12 ± 2 weeks; telephone contact is acceptable)

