12.3.4 Disease Control

Clinical efficacy will be evaluated using overall tumor response for participants with measurable disease as assessed by the investigators using RECIST v1.1 (Appendix B). Duration of response will be calculated for participants who achieve a CR or PR and is defined as the time from the date of first documented response (CR or PR) to the date of documented progression or death after achieving response. Progression-free survival will be calculated for all treated participants from the date of the first dose until the date of progression or death. Participants without progression or death will be censored at the date of last non-PD assessment. Overall survival will be calculated for all treated participants from the date of the first dose until date of death. Participants without death will be censored at the last date the participant was known to be alive. Disease control rate is defined as the percentage of participants who have achieved CR, PR, or SD lasting at least 12 weeks.

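### SAP 5.4.3 contradicts itself on which dates set the last-known-alive date; if its examination-only sentence is applied literally, telephone survival contacts are dropped and overall survival is biased downward

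*SAP*

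**What the plan says.** SAP 5.4.3 covers participants not known to have died. It sets the last-known-alive date "using the latest complete date among the following" and gives seven sources. Four of them need not involve an examination: "Last date collected on the 'Survival status' eCRF"; "Start and end dates of anti-cancer therapies administered after study treatment discontinuation"; adverse event dates; and the date of consent withdrawal.

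Below the list the section states: "Only dates associated with actual examinations of the participant will be used in the derivation". The next sentence is narrower: "Dates associated with a technical operation unrelated to participant status such as the date a blood sample was processed will not be used". The closing sentence, on the data cut-off, refers to the derived quantity as a date of last contact.

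SAP 7.1.2 censors OS at this date. Protocol 12.3.4 has no examination condition: "Participants without death will be censored at the last date the participant was known to be alive". SAP 1.2 declares no change from the protocol's analyses.

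Protocol Table 28, footnote p, has survival and new anti-cancer therapy assessed every 12 ± 2 weeks and says that "telephone contact is acceptable". Footnote i to the same table continues imaging in long-term follow-up until radiologic progression or new anti-cancer therapy.

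**The concern.** The word 'only' reads as a filter on everything above it. A survival call, a reported start of later therapy and a consent withdrawal are not examinations. One programmer could drop those dates and another keep them, and each could point to the SAP.

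If they are dropped, censoring depends on outcome. A death enters at its true date however it was learned of, so a participant who dies stays in the risk set until death. A participant still alive leaves the risk set at the last scan or clinic visit, even if a later call confirmed survival. Removing survivors early while keeping all deaths makes the Kaplan-Meier hazard too high and OS too low.

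The affected period could be long. The protocol cites a median PFS of 4 months on PLD (3.4) and a median OS of about one year on single-agent chemotherapy (3.8). If participants here are similar, much of survival falls after scheduled examinations end.

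**Working it through.** The documents give no target, power or expected estimate for OS, so there is no planned figure to reproduce. The check sizes the effect if the sentence overrides the list.

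**Inputs from the documents.** Median OS 12 months (protocol 3.8); median PFS 4 months (protocol 3.4); survival contact every 12 weeks (Table 28, footnote p); scans every 8 weeks (footnote i); safety follow-up visit 30 days after last treatment (footnote aa).

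**Assumptions.** Exponential times to death and progression; uniform accrual over 15 months; cut-off 3, 6, 12 or 24 months after last entry.

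**1. Closed-form check.** Suppose everyone is followed to month F and survivors are censored at a common last visit tc. A fraction S(F) then leaves at tc, and everyone left in the risk set dies before F. For t > tc:

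KM(t) = S(tc) × [S(t) − S(F)] / [S(tc) − S(F)], with S(t) = 0.5^(t/12).

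Setting KM = 0.5 gives S(t) = S(F) + 0.5 × [S(tc) − S(F)] / S(tc).

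- (tc, F) = (6, 18): S(6) = 0.707, S(18) = 0.354; S(t) = 0.354 + 0.250 = 0.604; median 8.7 months.
- (5, 18): median 8.3.
- (6, 24): median 9.6.
- (8, 18): median 9.6.
- (8, 24): S(8) = 0.630, S(24) = 0.250; S(t) = 0.250 + 0.302 = 0.552; median 10.3.

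The estimated median is therefore 8.3 to 10.3 months against a true 12. This overstates the effect, because every survivor has the same last visit and nobody continues scans.

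**2. Simulation with continuing scans.** Each scenario used 400,000 simulated participants. Deaths before cut-off always count. Living participants are censored either (a) at the last 12-weekly survival contact, or (b) at the last examination only, taken as progression plus one month, or as the last 8-weekly scan if not progressed. With true OS 12 and PFS 4 months:

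| Cut-off after last entry (months) | KM median, (a) contacts | KM median, (b) examinations only | Fall (before rounding) | 12-month OS, (a) | 12-month OS, (b) |
|---|---|---|---|---|---|
| 3 | 11.1 | 8.7 | 2.3 | 46.7% | 32.0% |
| 6 | 11.4 | 9.0 | 2.4 | 48.0% | 34.8% |
| 12 | 11.9 | 9.8 | 2.1 | 49.8% | 40.0% |
| 24 | 12.0 | 10.8 | 1.2 | 50.0% | 45.8% |

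**3. Sensitivity.** With OS 12 and PFS 5, the fall in the median is 0.9 to 1.8 months. With OS 15 (assumed) and PFS 5, it is 2.1 to 3.2 months. With 30 participants (OS 12, PFS 4), the typical median falls from 11.2 to 9.1 months at 6 months of follow-up, and from 12.0 to 9.8 at 12 months.

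**4. If the listed Survival status date is used,** column (a) applies. What remains is a small shortfall from the 12-week gap between contacts, at worst 11.1 against 12 at the shortest follow-up.

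**The case against.** The strongest reply is that the section as a whole points to the narrower meaning. The Survival status form is named as a source, and a reading that empties several entries of a purpose-built list is less likely than loose drafting. The sentence that follows describes the target as technical dates such as sample processing. The closing reference to a date of last contact also fits contact better than examination. Read that way, SAP 7.1.2 agrees with protocol 12.3.4.

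This stands as the likely intent. A reader might infer from the examination-only sentence that the SAP has settled on excluding telephone contacts and that survivors will be censored early. The documents do not support that, because the same section names the source that carries those contacts. Nor can one say that survival follow-up consists of telephone contacts: they are allowed, not required, and participants who have not progressed or started new therapy continue to have scans under any reading.

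The reply does not remove the contradiction. The sentence on technical dates is a separate exclusion and does not redefine an examination, and the SAP gives no rule for which text prevails.

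**Conclusion.** SAP 5.4.3 is internally inconsistent in an operative censoring rule, and the inconsistency should be removed. The downward bias and the departure from protocol 12.3.4 are conditional: they arise only if the sentence overrides the list. In that case the estimated median OS is about 1.2 to 2.4 months lower than with survival-contact censoring, for true medians of 12 months (OS) and 4 months (PFS). The size depends on the assumed accrual, cut-off and exponential times. The largest falls are at the shorter follow-ups, which matters because SAP 5.5 allows analyses before the final one.

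Severity is minor. OS is a secondary endpoint analysed descriptively, with no hypothesis or decision rule attached, and the Phase 2 criterion of at least six responses in 25 does not use it.

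**What to change.** Replace the examination-only sentence in SAP 5.4.3, together with the technical-dates sentence after it, with:

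> Dates on which the participant was seen, or was confirmed alive by any contact including telephone (Survival status eCRF), will be used; dates of technical operations (for example sample processing) will not.

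This makes the rule agree with its own source list and with protocol 12.3.4. The cost is one SAP sentence. It needs no new data collection and no protocol amendment, and SAP 1.1 allows the plan to be modified before database lock.

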5.5. Timing of Analyses

This is an exploratory study, so analyses may be performed as the study progresses, such as for the trial phase 2 transition. Efficacy and safety analysis for safety review/evaluation, and/or publication purposes might be produced before the final analysis (e.g. reporting for Phase 1 and Phase 2, separately).

5.6. Analysis Populations

5.6.1. Safety Analysis Set (SAS)

The safety analysis set will include participants who were enrolled and received at least one dose of PF-07901801. This analysis population will be the primary population for the analysis of safety and efficacy endpoints. For reporting response rate prior to study completion, the analysis population will include all patients with a baseline disease

Template No.: NVA_TP_CR694 Revision 4 Reference: SOPCR008, WPCR013 Template Effective Date:15Feb2023 Page 14 of 46

Pfizer Inc. / Protocol: C4971002 (TTI-622-02) IQVIA Biotech (Confidential) Project # ZZA82397

assessment, a follow-up assessment at least 4 weeks after the first dose and participants who have discontinued the study for any reason.

In Phase 1, each participant will be classified to a dose cohort if the initially planned PF-07901801 dose was received at least once any time on study. If the initially planned dose is never received by a participant, then the participant will be classified to the cohort based on highest PF-07901801 dose received.

For participants who received a wrong study dose, they would be recoded as protocol deviation, as described in section 6.3.

5.6.2. DLT-Evaluable Population (DLP)

The DLT-evaluable population is applicable to phase 1 dose-escalation participants only who either experience DLT after at least one dose of PF-07901801 or did not experience a DLT and received the full dose of PLD, at least two infusions of PF-07901801 and completed safety evaluations during the 28-day Cycle 1 DLT period.

5.6.3. PF-07901801 / PLD Concentration Analysis Population (PCP)

The PCP will include participants who received at least one dose of PF-07901801 and/or PLD and have at least one evaluable blood sample for analysis collected.

5.6.4. Immunogenicity Analysis Population (IAP)

The IAP will include participants who received at least one dose of PF-07901801 and with at least 1 anti-PF-07901801 antibody (ADA) and neutralizing anti-PF-07901801 antibody (NAb) sample analyzed (pre-dose or post-treatment).

If a subject has only pre-dose assessment and no post-treatment immunogenicity data, this subject is not evaluable for subject-level ADA and NAb evaluation, and should not be included in subject-level data analysis (e.g., overall ADA/NAb incidence, duration of ADA/NAb response).

5.6.5. Pharmacodynamics Analysis Population (PDP)

The PDP will include participants who received at least one dose of PF-07901801 and have at least one evaluable blood sample collected for specific biomarker and pharmacodynamics analysis (pre-dose or post-treatment).

If a subject has only pre-dose assessment and no post-treatment biomarkers and pharmacodynamics data, this subject is not evaluable for subject-level evaluation, and should not be included in the subject-level data analysis.

Template No.: NVA_TP_CR694 Revision 4 Reference: SOPCR008, WPCR013 Template Effective Date:15Feb2023

Pfizer Inc. / Protocol: C4971002 (TTI-622-02) IQVIA Biotech (Confidential) Project # ZZA82397

5.7. Data Display Characteristics

Data displays produced for this study will include three types—summary tables, data listings, and figures. Summary tables and figures will be produced when specified in sections to follow.

Data listings will list the data recorded on the CRF or derived for each subject. As needed, they can be produced by dose cohort, site, subject number, and time of assessment, and additional levels of ordering hierarchy may reflect subsets of assessments within subject. Subject-level identifiers appear on the first line of data, and identifiers for subgroups within subject appear only on the first line of each subgroup value.

Tables will display summary statistics calculated for each dose cohorts per study phase (escalation/expansion), unless described otherwise in the following sections. For most summary tables, the dose group will be presented in columns and the summary statistics of interest will be presented in rows.

The summary statistics displayed will be a function of the type of data associated with the summarized assessment. Unless stated otherwise in relevant sections to follow, continuous data will be summarized with the number of non-missing values, mean, standard deviation, minimum, median, and maximum. Categorical data will be summarized with the number of non-missing values and the numbers of values equal to each of the possible values. Percentages of subjects with each of the possible values will be calculated from the number of subjects in the corresponding analysis population, unless stated otherwise, and those percentages will be presented with one decimal (XX.X%). Some continuous variables may also be grouped into categorical levels and evaluated in frequency tables.

Dates in the clinical database are classified into the categories of procedure dates, log dates, milestone dates, outcome dates, and special dates:

- Procedure Dates (TARGET DATE): Dates on which given protocol-specified procedure are
 performed. They include the dates of laboratory testing, physical examinations, disease
 assessments, etc. They should be present whenever data for a protocol-specified procedure is
 present and should only be missing when a procedure is marked as NOT DONE in the database.
 Procedure dates will not be imputed.
- Log Dates: Dates recorded in CRF data logs. Specifically, they are the start and end dates for
 adverse events and concomitant medications/procedures. They should not be missing unless an
 event or medication is marked as ongoing in the database. Otherwise, incomplete log dates will be
 imputed according to the rules in Section 5.4.1 above. However, in listings, log dates will be shown
 as recorded without imputation.
- Milestone Dates: Dates of protocol milestones such as study drug start date, study drug termination date, study closure date, etc. They should not be missing if the milestone occurs for a subject. They will not be imputed.
- Outcome Dates: Dates corresponding to study endpoints such as survival, progression, etc. In most
 cases, they are derived either from a milestone (e.g., the survival date is derived from the death

Template No.: NVA_TP_CR694 Revision 4 Reference: SOPCR008, WPCR013 Template Effective Date:15Feb2023

Pfizer Inc. / Protocol: C4971002 (TTI-622-02) IQVIA Biotech (Confidential) Project # ZZA82397

date), or a procedure date (e.g., the progression date is derived from the date of the tumor scan that was used to determine progression). They may be subject to endpoint-specific censoring rules if the outcome did not occur but are not otherwise subject to imputation.

Special Dates: Dates that cannot be classified in any of the above categories and they include the
date of birth. They may be subject to variable-specific censoring and imputation rules.

Calculations using dates (e.g., subject's age or relative day after the first dose of study medication) will adhere to the following conventions:

- Trial Day 1 of Cycle 1 is defined as the day on which the dose of PLD and PF-07901801 is
 administered after screening. Study days after trial day 1 will be calculated as the difference
 between the date of interest and the first date of dosing of study medication plus 1 day. The
 generalized calculation algorithm for relative day: STUDY DAY = [(TARGET DATE DSTART)
 + 1 where DSTART = the start day of study drug].
- For dates of interest before the first date of dosing of study medication, the study day will be
 calculated as: STUDY DAY = TARGET DATE DSTART. Negative study days are reflective of
 observations obtained prior to first study drug administration. Note: Partial date for the first study
 drug is not imputed in general. All effort should be tried to avoid incomplete study drug start date.
- Age (years) at informed consent will be calculated as: (Date of informed consent date of birth +
 1) / 365.25, and then truncated to an integer. In case of partial birth date: impute missing day as
 15th of the month; impute missing month as July (7th month); set missing age in case of missing
 year.
- Duration will be calculated by the difference of start and stop date + 1. AE duration (days) = AE
 end date AE start date +1
- Study drug exposure duration (weeks) is detailed in section 8.1. Exposure.
- Time since disease diagnosis (months) will be calculated as (Informed Consent Date Diagnosis Date + 1) / 30.4167.
- The time to event will be calculated as date of event minus reference date + 1. The specific
 censoring rules on time to event endpoints will follow Section 7.1.1. Secondary Efficacy Outcome
 Analysis, and Section 8.7. ECOG Performance Status.
- The following conversion factors will be used to convert days to months or years:
 - 1 month = 30.4167 days
 - 1 week = 7 days
 - 1 year = 365.25 days

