8.6. Clinical Laboratory Results

Clinical laboratory tests (serum chemistry and hematology) will be performed at screening and, generally, each day receiving a PF-0790180 dose, unless otherwise specified in table 28. Schedule of Assessment, of the protocol. Baseline laboratory measurements do not need to be repeated if screening measurements were performed within 3 days prior to Cycle 1 Day 1. All laboratory data will be converted to standardized conventional units for reporting purposes.

Serum chemistry tests include determination of the following parameters: glucose, sodium, potassium, calcium, chloride, phosphate, bicarbonate, blood urea nitrogen or urea, creatinine, total protein, albumin, alkaline phosphatase, aspartate aminotransferase (AST), alanine aminotransferase (ALT), total bilirubin, indirect bilirubin, uric acid, calcium, magnesium, and lactate dehydrogenase (LDH).

Hematology tests include determination of the following parameters: Hemoglobin, hematocrit, platelets, white blood cells (WBC), neutrophils, lymphocytes, eosinophils, basophils, monocytes, WBC with automated 5-part differential, red blood cells (RBC), absolute reticulocytes, reticulocytes %, Erythrocyte Mean Corpuscular Hemoglobin (MCH), Erythrocyte Mean Corpuscular Volume (MCV), and Red Cell Distribution Width (RDW).

Summaries of baseline values and changes from baseline will be presented by dose level for each assessment time point.

Serum chemistry and hematology evaluations which cannot be graded per CTCAE criteria will be summarized as counts and percentages of participants who were normal at baseline, but who became abnormal subsequently.

For serum chemistry and hematology evaluations which can be graded per CTCAE v5.0, the following summary table will be created:

- Shift summary of baseline CTCAE grade versus the worst on-treatment CTCAE grade (The highest CTCAE grade during the on-treatment period is considered as the worst grade [Grade 0, 1, 2, 3, or 4] for the summary)
- Shift summary from ≤ Grade 2 at baseline to ≥ Grade 3 postbaseline

Clinical laboratory results will be listed by participant. In addition, listings of abnormal values will be provided for hematology, chemistry, coagulation parameters. If there is at least one abnormal assessment for any parameter, all the data for that laboratory parameter will be included into the listing.

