8.9. Electrocardiogram (ECG)

Supine position 12-lead ECGs will be performed at screening and reviewed locally at each visit. An overall interpretation of the ECG results will be made (normal/abnormal), and corrected QT intervals, will be summarized by visit.

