55Mean and Change in Vital Signs Over TimeSAS56ECG Abnormalities, Number (%) of ParticipantsSAS57CA-125 Concentrations, by Dose Cohort and CyclePDP58Pharmacodynamic Biomarkers Concentrations, by Dose Cohort and CyclePDP59Mean Change in Pharmacodynamic Biomarkers, by Dose Cohort and CyclePDP60Incidence and Duration of ADA and NAb, by Dose CohortIAP61Serum PF-07901801 Concentrations, by Dose Cohort, Visit and Timepoint: Summary StatisticsPCP			SAS
56 ECG Abnormalities, Number (%) of Participants SAS 57 CA-125 Concentrations, by Dose Cohort and Cycle PDP 58 Pharmacodynamic Biomarkers Concentrations, by Dose Cohort and Cycle PDP 59 Mean Change in Pharmacodynamic Biomarkers, by Dose Cohort and Cycle PDP 60 Incidence and Duration of ADA and NAb, by Dose Cohort IAP 61 Serum PF-07901801 Concentrations, by Dose Cohort, Visit and Timepoint: Summary Statistics PCP			SAS
57 CA-125 Concentrations, by Dose Cohort and Cycle PDP 58 Pharmacodynamic Biomarkers Concentrations, by Dose Cohort and Cycle PDP 59 Mean Change in Pharmacodynamic Biomarkers, by Dose Cohort and Cycle PDP 60 Incidence and Duration of ADA and NAb, by Dose Cohort IAP 61 Serum PF-07901801 Concentrations, by Dose Cohort, Visit and Timepoint: Summary Statistics PCP			
58 Pharmacodynamic Biomarkers Concentrations, by Dose Cohort and Cycle PDP 59 Mean Change in Pharmacodynamic Biomarkers, by Dose Cohort and Cycle PDP 60 Incidence and Duration of ADA and NAb, by Dose Cohort IAP 61 Serum PF-07901801 Concentrations, by Dose Cohort, Visit and Timepoint: Summary Statistics PCP		ECG Abnormalities, Number (%) of Participants	SAS
59 Mean Change in Pharmacodynamic Biomarkers, by Dose Cohort and Cycle PDP 60 Incidence and Duration of ADA and NAb, by Dose Cohort IAP 61 Serum PF-07901801 Concentrations, by Dose Cohort, Visit and Timepoint: Summary Statistics PCP		CA-125 Concentrations, by Dose Cohort and Cycle	PDP
60 Incidence and Duration of ADA and NAb, by Dose Cohort IAP 61 Serum PF-07901801 Concentrations, by Dose Cohort, Visit and Timepoint: Summary Statistics PCP			
61 Serum PF-07901801 Concentrations, by Dose Cohort, Visit and Timepoint: Summary Statistics PCP	59	Mean Change in Pharmacodynamic Biomarkers, by Dose Cohort and Cycle	PDP
	60	Incidence and Duration of ADA and NAb, by Dose Cohort	IAP
62 Serum PLD Concentrations, by Dose Cohort, Visit and Timepoint: Summary Statistics PCP			
	62	Serum PLD Concentrations, by Dose Cohort, Visit and Timepoint: Summary Statistics	PCP

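### SAP 8.6 and 8.9 do not override the 5.7 default denominator, so by-visit ECG abnormality and normal-to-abnormal laboratory percentages are diluted by participants not assessed or not at risk

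*SAP*

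**What the plan says.** SAP 5.7 has two relevant rules for categorical tables. On counts: "Categorical data will be summarized with the number of non-missing values and the numbers of values equal to each of the possible values". On percentages: "Percentages of subjects with each of the possible values will be calculated from the number of subjects in the corresponding analysis population". The same sentence goes on to allow exceptions where they are stated, so the second rule is a default that a later section may replace.

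SAP 5.6.1 defines the population used for safety tables: "The safety analysis set will include participants who were enrolled and received at least one dose of PF-07901801". SAP 5.4 rules out imputation except for partial dates, so a missed visit stays missing.

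Two sections produce the percentages at issue:

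- SAP 8.9, on ECG: "An overall interpretation of the ECG results will be made (normal/abnormal), and corrected QT intervals, will be summarized by visit". The output is Table 56, "ECG Abnormalities, Number (%) of Participants", with SAS as its population.
- SAP 8.6, on laboratory tests that CTCAE cannot grade: these are reported as "counts and percentages of participants who were normal at baseline, but who became abnormal subsequently". The outputs are Table 48 (chemistry) and Table 51 (hematology), both on SAS.

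Neither section names a denominator. Elsewhere the SAP does state its base: 5.6.4 and 5.6.5 remove participants without post-treatment data from subject-level immunogenicity and pharmacodynamic analyses, section 8 puts DLTs on the DLT-evaluable population, and 7.1.1 deliberately keeps every SAS participant in the response denominator.

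**The concern.** A programmer following the SAP as written would divide by all SAS participants in Tables 48, 51 and 56.

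- **ECG by visit.** ECGs continue at Cycle 4, Cycle 7 and every second cycle after that (Protocol Table 28), when some participants will have left treatment. They have no result but remain in the denominator, so the abnormal percentage can fall from visit to visit simply because people leave.
- **Laboratory tests without grades.** A participant already abnormal at baseline cannot move from normal to abnormal, and one with no later sample cannot be seen to do so. Both still count in the denominator.

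ECG and laboratory changes belong to the secondary safety endpoint (Protocol 4.4, SAP 3.2). LVEF is scheduled only at screening and repeated if clinically indicated (Protocol 9.2.5), so ECG is the cardiac test that recurs on a fixed schedule. What is at stake is whether the printed safety percentages mean what a reader will take them to mean.

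**Working it through.** The documents state no figure that depends on this rule, so there is nothing to reproduce. The check has a textual part and an illustration of size.

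**Which denominator applies.** The 5.7 default is the analysis population. Sections 8.6 and 8.9 give no other base, and Appendix 1 lists SAS for Tables 48, 51 and 56. The default therefore governs these outputs. The 8.6 wording could be read as restricting the base to participants normal at baseline, but it does not say so.

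**Formula.** Let x be the number with the event, N the SAS count, and n the number assessed at the visit (ECG) or normal at baseline with at least one later value (laboratory). Then

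printed percentage = x/N = (x/n) × (n/N).

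The rate among those assessed or at risk is multiplied by n/N. If n = N there is no bias.

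**ECG, illustration by attrition.** Inputs:

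- Median time on treatment: 4 months, borrowed from the median PFS with PLD in Protocol 3.4, and 6 months as an upper value (Protocol 3.8 puts single-agent PFS below six months). Using PFS for time on treatment, with exponential loss, is an assumption.
- Abnormality rate among those assessed: 20% (assumption).
- 1 month = 30.4167 days (SAP 5.7).

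Share remaining = 0.5^(months/median). Week 12 (Cycle 4 Day 1) is 84/30.4167 = 2.76 months; Week 24 (Cycle 7 Day 1) is 168/30.4167 = 5.52 months.

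| Median (assumed) | Share at Week 12 | 20% prints as | Share at Week 24 | 20% prints as |
|---|---|---|---|---|
| 4 months | 0.620 | 12.4% | 0.384 | 7.7% |
| 6 months | 0.727 | 14.5% | 0.528 | 10.6% |

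**ECG, illustration by counts.** In a cohort of 25 (the planned expansion size) with 3 abnormal ECGs at a late visit, the table prints 3/25 = 12.0%. Among those assessed the rate is 3/20 = 15.0%, 3/15 = 20.0% or 3/10 = 30.0%, for 20, 15 or 10 assessed (assumed).

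**Laboratory, illustration by counts.** With N = 25 and 5 participants moving from normal to abnormal (assumed), the table prints 5/25 = 20.0%.

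| Normal at baseline with a later value (assumed) | Rate among those at risk |
|---|---|
| 25 | 20.0% |
| 22 | 22.7% |
| 20 | 25.0% |
| 15 | 33.3% |
| 10 | 50.0% |

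**The case against.** The strongest reply is that 5.7 already displays the non-missing count. A by-visit ECG table would show how many were assessed, how many were normal and how many abnormal, so a reader can compute abnormal over assessed. Absent participants are not counted as normal either: the normal percentage shrinks too, and the two fail to reach 100%. This stands for ECG. It does not rescue the laboratory tables, because the non-missing count does not show how many were normal at baseline.

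It can also be said that the laboratory outputs are titled as shift tables and their shells are not in the documents, so baseline-row counts might appear. They might, but the SAP text does not require them. Participant-level laboratory listings are planned and the medical monitor reviews laboratory and ECG data (SAP 8.6, Protocol 13.11). That protects safety oversight, but it does not correct a printed percentage.

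The sizes above are arithmetic on assumed rates and assumed attrition. Treatment may continue past progression or stop earlier for toxicity (Protocol 5.3), so PFS is only a rough stand-in for time on treatment.

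A reader might infer three stronger points, which the documents do not support:

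- **That every categorical percentage is affected.** The rule can be overridden and is, in 5.6.4 and 5.6.5. For response, the full SAS denominator is an explicit and appropriate choice.
- **That the shift from Grade 2 or lower to Grade 3 or higher is diluted in the same way.** For the key blood counts, entry limits (ANC 1.5 and platelets 100 × 10⁹/L, hemoglobin 9 g/dL; Protocol 6.2) lie above the Grade 3 cut-offs in Protocol Table 27 (ANC below 1, platelets below 50, hemoglobin below 8). Nearly everyone enters at risk, so the baseline bias is about zero. Samples on Days 8, 15 and 22 of Cycle 1 should also make a missing later value rare.
- **That RP2D selection is distorted.** No section bases it on these percentages. Cohort review uses DLT incidence, treatment-related safety observations and other data such as PK after the 28-day window (Protocol 5.1, 13.12).

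**Conclusion.** The point holds for two sets of outputs: by-visit ECG normal/abnormal percentages (Table 56) and normal-to-abnormal percentages for laboratory tests without CTCAE grades (Tables 48 and 51). Under the SAP as written, each is understated by the factor n/N, where n is the number assessed or at risk.

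The size depends on attrition and on baseline status, which the documents do not give. Under exponential loss with a 4 to 6 month median, a 20% ECG abnormality rate would print as about 7.7% to 10.6% at Week 24. With complete assessment and all baselines normal, nothing changes. The ECG rate can be recovered from the displayed non-missing count. The laboratory rate cannot be recovered from that count.

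This is a minor issue in descriptive safety tables. No efficacy result is affected.

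**What to change.** - **SAP 8.9:** state that by-visit ECG percentages use participants with a non-missing result at that visit.
- **SAP 8.6:** state that normal-to-abnormal percentages use participants who were normal at baseline and have at least one post-baseline value.
- **Both:** show n/N in each cell.
- **Unchanged:** keep the SAS denominator for ORR, BOR and TEAE incidence.

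The cost is two sentences and minor programming, with no new data. SAP 1.1 allows changes before database lock. The drawback is that the percentages will rest on smaller and varying denominators, which the n/N display makes plain.
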